#### **Renefits:**

There are possible benefits to participants of this study. All participants will help researchers better understand stigma, coping self-efficacy, ART medication adherence, engaging in care, sexual risk behaviors and quality of life. Completion of study instruments will allow the women an opportunity to express past/recent experiences. Participants will receive the equivalent of \$8USD to \$13USD for their time (lost wages) and to cover travel associated costs. The risks to participants are both minimal and reasonable in relation to the anticipated benefits to participants and others.

#### **Costs to the Subject**

Describe and justify any costs that the subject will incur as a result of participation; ordinarily, subjects should not be expected to pay for research without receiving direct benefit.

Participants in this study will not incur any costs.

## **Data Analysis & Statistical Considerations**

Describe endpoints and power calculations. Provide a detailed description of how study data will be analyzed, including statistical methods used, and how ineligible subjects will be handled and which subjects will be included for analysis. Include planned sample size justification. Provide estimated time to target accrual and accrual rate. Describe interim analysis including plans to stop accrual during monitoring. Phase I studies, include dose escalation schema and criteria for dose escalation with definition of MTD and DLT.

#### STATISTICAL DESIGN AND POWER

**Power Analysis.** The proposed study is designed to assess the preliminary efficacy of the intervention and to generate pilot data to support the conduct of a larger trial. The sample size of 160 is, therefore, primarily determined by whether the intervention could be feasibly implemented in a larger, multi-site study and to calculate a pooled effect size for the primary outcomes so as to determine the sample size necessary for such a large study, rather than by the power to detect specified effect sizes. Nevertheless, we have conducted a power analysis using the Optimal Design for mixed effects models on repeated measures of continuous outcomes, employing an intention-to-treatment analysis. The power analysis revealed that a total sample size of 160 (i.e, 80 in each treatment arm) would achieve 80% power to detect a standardized effect size  $\delta$  of 0.51 with four repeated measurements, assuming an intra-class correlation of 0.70 and a two-tailed alpha of .05. The standardized effect size  $\delta$  is analogous to Cohen's d for which Cohen defines 0.20 as a small effect, 0.50 as a medium effect size, and 0.80 as a large effect. Thus, we will have sufficient power to detect a medium effect size of the longitudinal intervention effect on a linear trend of stigma, coping self-efficacy, and self-esteem over time. For comparing intervention effects at days 30, 90, and 180, cross-sectionally, the results from another power analysis with the  $G^*Power^{49}$  on independent-sample tests show that we will have 80% power to detect a close to medium effect size of Cohen's d = 0.45. Additionally, we expect the dropout rate will be less than 10% based on studies we have conducted in this area, and attrition between conditions will not differ. The sample size will not require an attrition adjustment because mixed-effects models allow for data missing at random.

**Statistical Analysis, Aim #1, Feasibility:** To assess the feasibility, the following parameters will be collected and evaluated:

•Recruitment: to identify the length of time to complete participant recruitment; identify barriers to recruitment; to assess the number of participants who meet screening criteria (median score of IHSS) to meet sample size estimation; to determine capacity to recruit women who may not be engaged in care •Retention: to assess adherence to and completion of the intervention (high-intensity intervention), attendance and punctuality for group intervention sessions

•Measurement: to assess the time (minutes) it takes to complete the questionnaires; to evaluate missing data from questionnaires

•Fidelity: to evaluate fidelity to study protocol and structured debriefing using Motivational Interviewing will be done using detailed fidelity checklists. These fidelity checklists will evaluate delivery of a list of important teaching components in each session

•Process Evaluation: to conduct a qualitative evaluation with participants to identify barriers and facilitators, perceptions, and overall satisfaction with the *Labda Siku Moja* intervention

Statistical Analysis, Aim #2: We will conduct an intention-to-treat analysis which will include all women randomized to determine whether women living with HIV who viewed the video experience a greater reduction in internalized stigma and greater improvements in coping self-efficacy and self-esteem over the 180 days than women in the control condition. Two-tailed statistical tests will be performed using SAS 9.4. For this exploratory study, the significance level will not be adjusted for multiple tests. Student *t*-tests and chi-square tests will be used to test whether the randomization balanced the conditions on key baseline characteristics and baseline scores on the main outcomes. If treatment conditions differ significantly on any these characteristics, which is unlikely to happen though due to the random assignment, the baseline measure would be controlled as a covariate in subsequent analyses. Random coefficients regression models (a type of hierarchical mixed effects model for repeated measures) will be used to examine between-condition differences in change over time (trajectories across baseline, 30 days, 90 days, and 180 days) in the outcomes. Fixed effects will be condition, time, and condition-by-time, while random effects will be participant and participant-by-time. If necessary, baseline covariates will be included as fixed effects. We will also conduct a priori contrasts to examine differences between treatment conditions at 30, 90, and 180 days. Observed effect sizes will be calculated for the condition-by-time effects (rate of change) and between-condition differences at 30, 90, and 180 days.

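### The reason given for making no attrition adjustment concerns bias, not precision; the detectable effects of 0.51 and 0.45 are complete-data figures and should be restated for up to 10% dropout

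*Combined protocol and SAP*

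**What the plan says.** All the power statements are in the Power Analysis paragraph under STATISTICAL DESIGN AND POWER. With 160 women, 80 per arm, the plan gives two detectable effects at 80% power:

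- Longitudinal: a standardised effect "of 0.51 with four repeated measurements, assuming an intra-class correlation of 0.70 and a two-tailed alpha of .05". From this it claims "sufficient power to detect a medium effect size of the longitudinal intervention effect on a linear trend".
- Single visit (day 30, 90 or 180): the G*Power results "on independent-sample tests show that we will have 80% power to detect a close to medium effect size of" Cohen's d = 0.45.

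On dropout it says "we expect the dropout rate will be less than 10% based on studies we have conducted in this area", assumes equal attrition in the two arms, and concludes: "The sample size will not require an attrition adjustment because mixed-effects models allow for data missing at random".

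The same paragraph says that N was set mainly by feasibility and by the need to estimate an effect size for a larger trial, "rather than by the power to detect specified effect sizes".

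Under Statistical Analysis, Aim #2, the efficacy model is a random coefficients regression: "Fixed effects will be condition, time, and condition-by-time, while random effects will be participant and participant-by-time". It adds: "We will also conduct a priori contrasts to examine differences between treatment conditions at 30, 90, and 180 days".

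No detectable effect net of dropout is given anywhere. The allowance to consent as many as 200 women (Design & Procedures; Study Sample Recruitment) is for screen failures, so it is no cushion against attrition.

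**The concern.** The argument treats two different properties as one. A likelihood-based mixed model gives valid estimates when data are missing at random; that is a statement about bias. Precision depends on how much is observed, and a woman who leaves contributes less information than one who completes.

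The reason fits the single-visit figure least well. An independent-sample test uses only the women observed at that visit, so a property of mixed models cannot protect it. For the trend test the mixed model does use the early visits of women who leave. A woman seen only at baseline, however, tells it almost nothing about her slope.

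At stake are the claims of 80% power and of sufficient power for a medium effect, which should hold under the plan's own dropout assumption. The trial is also meant to inform the sample size of a larger study. The same reasoning carried forward would size that study with no allowance for lost precision.

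**Working it through.** **Inputs from the plan:** 80 women per arm, two-sided alpha 0.05, 80% power, d = 0.45 at one visit, delta = 0.51 for the trend, intra-class correlation 0.70, visits at 0, 30, 90 and 180 days, dropout below 10% and equal between arms.

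**1. Single visit: reproduce 0.45.** For a two-sample t-test with n per arm, power is the probability that a noncentral t variable with 2n − 2 degrees of freedom and noncentrality d√(n/2) exceeds the two-sided critical value. At n = 80 the noncentrality is 0.45 × √40 = 2.846 and the critical value is 1.975 (158 df). Power is 80.8% and the detectable d is 0.446. The plan's figure is reproduced with everyone observed.

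**2. Single visit with dropout.** Observed women per arm: 80 × 0.95 = 76 and 80 × 0.90 = 72.

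| Observed per arm | Power at d = 0.45 | Detectable d at 80% power | Power at d = 0.50 |
|---|---|---|---|
| 80 | 80.8% | 0.446 | 88.2% |
| 79 | 80.3% | 0.449 | 87.8% |
| 78 | 79.7% | 0.451 | 87.3% |
| 76 (5% loss) | 78.7% | 0.457 | 86.5% |
| 72 (10% loss) | 76.5% | 0.470 | 84.6% |

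Losing two women per arm (2.5%) already takes power just below 80%.

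**3. Trend test: what can be reproduced.** The plan does not state the variance components or time coding behind 0.51. One assumed reading (slope variance 0.70, residual variance 1, four equally spaced visits, N = 160) gives 0.505. Other readings of the 0.70 give 0.39 to 0.53. I therefore take 0.51 at 80% power on complete data as given and compute only the proportional change.

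**4. Trend test with dropout.** Assumptions: intercept variance 0.70 and residual variance 0.30 (from the stated correlation), slope variance 0, 0.1, 0.3 or 0.7, no intercept–slope covariance, visits at 0/30/90/180 days scaled to 0–1, and equal loss in both arms. For a woman with visit design Z (intercept and time), the information is Z′V⁻¹Z with V = ZGZ′ + 0.30·I. Information is summed over completers and leavers and inverted. Let r be the slope standard error divided by its complete-data value. Then power = Φ(2.802/r − 1.960), where 2.802 = 1.960 + 0.842, and the detectable effect is 0.51 × r.

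| 10% loss, all leaving | r | Power at 0.51 | Detectable effect |
|---|---|---|---|
| after baseline | 1.049–1.052 | 75.9–76.1% | 0.535–0.537 |
| after day 30 | 1.049–1.050 | 76.0–76.1% | 0.535–0.536 |
| after day 90 | 1.031–1.040 | 76.8–77.5% | 0.526–0.530 |
| spread equally over the three | 1.044–1.046 | 76.4–76.5% | 0.533 |

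At 5% loss, r is 1.015–1.025, power is 78.0–78.8% and the detectable effect is 0.518–0.523.

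The ceiling, if leavers contributed nothing, is r = √(160/144) = 1.054. That gives 0.51 × 1.054 = 0.538 and power of about 76%. Under the equally spaced reading in step 3, with intercept variance 0.70 (assumed), r at 10% loss runs from 1.01 (all leave after the third visit) to 1.05 (all leave after baseline).

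**5. Visit contrasts inside the mixed model.** Same assumptions, d = 0.45 scaled to the SD at each visit, 10% loss, normal approximation. With categorical time, power is 78.2–81.2% (81.2% on complete data). With linear time it is 79.3–89.5% (82.4–89.7% on complete data).

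**The case against.** The strongest reply is that the disputed sentence is about sample size, and its conclusion is acceptable. N was chosen for feasibility, the power analysis is supplementary, and nobody is asking for more women. That stands, and it is why this is a correction to a stated justification and two stated figures, not to the design.

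Second, the planned day 30/90/180 contrasts accompany a mixed model and are not presented as complete-case t-tests. Step 5 shows that, taken from the model, they lose little at 10% dropout. That also stands. But the plan attributes 0.45 to an independent-sample test, and on those terms the figure does not survive 10% loss.

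Third, 10% is a ceiling. At 5% loss the detectable d is 0.457, and the plan's wording of medium and close to medium largely survives. This is agreed. The plan nevertheless states numbers and an 80% power level, and those hold only with essentially complete data.

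Fourth, the inputs behind 0.51 are not stated, and the spread across possible readings (0.39–0.53) exceeds the shift at issue. So 0.53–0.54 is conditional on the assumptions above. The direction is not: every dropout pattern and variance tried gave a loss, with a ceiling of about 5%.

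Finally, all these figures treat women as independent although the intervention is delivered in groups. That is a separate matter, but the restated text should say so.

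**Conclusion.** The concern holds. Missing-at-random validity is not a reason to leave complete-data detectable effects unadjusted, and nothing else in the document allows for dropout. The complete-data figures of 0.45 and 0.51 are not claimed to be wrong.

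At the plan's 10% ceiling the loss is about 4 percentage points of power for the single-visit test. That result rests only on the plan's own inputs and on treating women as independent. For the trend test the loss is about 2.5 to 4 points, which rests on the assumed variance components, visit scaling and dropout timing; a loss concentrated after the third visit under the equally spaced reading would be smaller. The effect on the trial is minor, and the correction is worth making because it is cheap and the present sentence is wrong as written.

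**What to change.** Keep N = 160 and the analysis. Replace the attrition sentence with wording such as:

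> Mixed models use all available data under missing at random but do not recover precision lost to dropout. With up to 10% dropout (72 per arm), and treating women as independent, an independent-sample comparison at one visit has 80% power for d of about 0.47 (0.46 at 5% loss).

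Rerun the longitudinal power calculation for visits at 0, 30, 90 and 180 days with up to 10% dropout. Report the detectable effect with the assumed variance components and dropout timing. If the single-visit claim is meant to describe the contrasts from the mixed model, say so and give that figure as well.

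The cost is one sentence and one rerun. The stated detectable effects become slightly less favourable. No participants are added.

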## Inclusion Criteria.

The inclusion criteria for this study are: (1) women who are living with HIV; (2) age 18 (age of adulthood as defined by the Tanzanian government); (3) able and willing to voluntarily consent to participate in the study; (4) able to travel to a data collection in their local community (as described above); (5) demonstrate mental competence at time of informed consent; (6) verbally indicate that they plan to reside in their current community for at least 6 months after enrollment (necessary to prevent attrition); and (7) score at the median or higher level on the Swahili Version of the Multidimensional Measure of Internalized HIV Stigma Scale.

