## Compensation.

UPDATED, 8 September 2022:

All women who are screened for the study, will receive an incentive as described below:

- not eligible-get incentive (\$2.50)
- eligible-decline enrollment-get incentive (\$2.50)
- eligible-enroll-complete rest of questionnaire-get incentive (\$5)

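### Baseline adjustment hangs on a significance test and, when triggered, enters as a main effect that largely corrects the visit contrasts but not the rate of change

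*Combined protocol and SAP*

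**What the plan says.** The plan is under STATISTICAL DESIGN AND POWER, in the paragraph Statistical Analysis, Aim #2.

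- **Trigger.** Balance is tested with Student t-tests for means; in addition, "chi-square tests will be used to test whether the randomization balanced the conditions on key baseline characteristics and baseline scores on the main outcomes". When the arms differ significantly, "which is unlikely to happen though due to the random assignment, the baseline measure would be controlled as a covariate in subsequent analyses".
- **Form of the covariate.** "If necessary, baseline covariates will be included as fixed effects". No covariate-by-time term is named.
- **Model.** "Fixed effects will be condition, time, and condition-by-time, while random effects will be participant and participant-by-time".
- **Responses.** The outcome is modelled as "trajectories across baseline, 30 days, 90 days, and 180 days", so baseline is itself a response. Design & Procedures gives the same four time points.
- **Reported results.** "Observed effect sizes will be calculated for the condition-by-time effects (rate of change) and between-condition differences at 30, 90, and 180 days".

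The Power Analysis paragraph adds that the 160 women are there chiefly to show feasibility and to supply effect sizes for sizing a larger trial. It assumes 80 per arm, an intra-class correlation of 0.70, two-sided alpha of 0.05 and dropout below 10%.

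**The concern.** Three things follow from this text.

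1. In a randomized trial a baseline difference between arms is chance. Testing it answers no useful question, yet here the test result selects the model.
2. When the test is significant for an outcome's own baseline score, the text promises that the imbalance is controlled. A time-constant main effect moves the level difference between arms but not the difference in slope. Part of any chance gap closes at follow-up through regression to the mean, and that closing is counted as a difference in rate of change.
3. When the test is not significant, the smaller gap is left wholly unadjusted in the three visit contrasts.

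At stake are the effect sizes that the plan intends to carry into the design of a larger trial. If the intervention arm happens to start with higher stigma, the rate of change exaggerates the reduction. If it starts lower, it understates it.

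**Working it through.** **Inputs from the plan.** 80 per arm; two-sided 0.05; visits at 0, 30, 90 and 180 days, coded t = 0, 1/6, 1/2, 1; random intercept and slope; dropout below 10%. As a check on these inputs, 80 per arm gives 80.8% power at d = 0.45 by the noncentral t, with a detectable d of 0.446 at 80% power. This agrees with the plan's cross-sectional figure.

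**Assumptions.** Linear time, and an equal correlation r between any two visits. The plan does not define its 0.70 as the baseline-to-follow-up correlation, so r = 0.3 to 0.8 is shown. Units are baseline SDs.

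**How often, and how large a gap.** The SD of the baseline gap is √(2/80) = 0.158.
- Smallest significant gap: 1.96 × 0.158 = 0.310.
- Trigger probability: 5% per outcome; for at least one of three, if independent, 1 − 0.95³ = 14%.
- Mean gap when triggered: 0.1581 × 0.05845 / 0.025 = 0.370.
- Mean gap when not triggered: 0.1581 × 2 × (0.3989 − 0.0584) / 0.95 = 0.113.

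**Slope shift with no true effect.** Mean t is 0.4167 and the sum of squares about it is 0.5833. The slope weight on baseline is −0.4167/0.5833 = −0.714. A gap g at baseline is expected to be r·g at each later visit, so the fitted slope shifts by −0.714(1 − r)g. With g = 0.370:

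| r | 0.3 | 0.5 | 0.7 | 0.8 |
|---|---|---|---|---|
| shift per 180 days (SD) | −0.18 | −0.13 | −0.08 | −0.05 |

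**What the covariate does to the slope.** With complete data on common visits, each woman's slope depends in this model on condition alone, and a time-constant term enters only her level. Over 200 random covariance structures the condition-by-time estimate moved by at most 1.6 × 10⁻¹⁵. In 800 simulated null trials with a significant baseline test at r = 0.70 and 8.8% dropout (REML), the mean slope was −0.085 without the covariate, −0.083 with it, and −0.002 with a common baseline mean (simulation SE 0.004).

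**What it does to the visit contrasts.** The share of the gap carried to visit t without adjustment is r + (1 − r)[1/4 − 0.4167(t − 0.4167)/0.5833]. At r = 0.70 this is 0.829, 0.757 and 0.650 at days 30, 90 and 180.
- Triggered, no covariate: × 0.370 = 0.31, 0.28 and 0.24.
- Triggered, with covariate (800 simulated trials, complete data): 0.002, −0.023 and −0.059. With dropout, day 180 is −0.072.
- Not triggered: × 0.113 = 0.09, 0.09 and 0.07 on average; × 0.310 = 0.26, 0.23 and 0.20 at most.

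**Scale.** The planned slope variance is (2/80)(1 − r)/0.5833. At r = 0.70 this is 0.01286, so the SE is 0.113 and the 95% half-width is 1.96 × 0.113 = 0.22. The shift of 0.08 is about a third of that half-width. In triggered trials at 0.70, slope type I error is 7–10% without the covariate and 5–6% with it. Over all trials it stays near 5%.

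**Precision of the alternative.** With a common baseline mean, slope variance relative to the plan is 1 − 0.5102(1 − r)/{1.7143[r + 0.5476(1 − r)]}, which is 0.90 at r = 0.70 and 0.81 at 0.5. For visit contrasts with categorical visit and a common baseline mean, variance is (2/80)(1 − r²). The planned linear contrast has (2/80){r + (1 − r)[1/4 + (t − 0.4167)²/0.5833]}. Ratios at days 30, 90 and 180:

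| r | day 30 | day 90 | day 180 |
|---|---|---|---|
| 0.7 | 0.63 | 0.66 | 0.54 |
| 0.5 | 1.10 | 1.19 | 0.82 |
| 0.3 | 1.65 | 1.88 | 1.03 |

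**The case against.** The strongest reply is that this is small and rare, and that the planned rule mostly works. The shift arises in 5% of trials per outcome and is well inside the interval that a pilot of this size will report. The study calls itself exploratory. When the rule fires, the three visit contrasts are largely corrected and slope type I error in those trials returns close to nominal. All of this stands.

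The text can also be read more generously. Calling covariates fixed effects may only distinguish them from the random effects, and so need not exclude a baseline-by-time term, which would correct the slope. Nor does the text rule out dropping baseline as a response once it becomes a covariate. That would turn the effect into a slope over days 30 to 180 only. Neither option is stated, so what can be said is that the remedy as written does not reach the slope and that its form needs specifying.

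A reader might infer that the stated adjustment is useless. The visit contrasts show that it is not. A reader might also infer the same slope shift for an imbalance in any tested characteristic. The calculation covers only an outcome's own baseline score, and nothing is shown for others.

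Finally, eligibility requires women to "score at the median or higher level on the Swahili Version of the Multidimensional Measure of Internalized HIV Stigma Scale", and one might add the effect of that truncation. The Compensation section describes enrolled women only as "eligible-enroll-complete rest of questionnaire-get incentive". The documents do not say that the screening score serves as the baseline outcome score, so no figure is built on it.

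**Conclusion.** The point holds as one of specification, with a modest numerical consequence. The significance trigger should go whatever view is taken of the slope. The plan's covariate, read as a main effect with baseline still a response, leaves the condition-by-time estimate exactly unchanged with complete data and nearly unchanged with the expected dropout. In triggered trials the reported rate of change then carries about −0.08 SD per 180 days for each outcome concerned at r = 0.70, with a range of −0.18 to −0.05. In the other trials, smaller gaps stay in the visit contrasts as avoidable sampling error.

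A reader might infer that the trial's effect sizes are biased or its tests invalid. They are not: averaged over randomizations there is no bias. The fault lies in the estimate given the imbalance actually observed, and in a text that says it has been controlled. The sizes rest on assumed correlations, equal correlation across visits and linear time. The invariance with complete data does not.

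**What to change.** - Delete the significance trigger. Describe baseline by arm without p-values.
- Prespecify adjustment for each outcome's own baseline in every analysis, and name any other covariates in advance.
- For condition-by-time, keep all four time points as responses for everyone randomized and constrain the arms to a common baseline mean.
- Take the 30, 90 and 180-day contrasts from the same four-response, common-baseline model with visit as categorical, and say so. They should not be read from the linear common-mean version, where they are simply the slope times 1/6, 1/2 and 1. At r = 0.70, an effect of 0.5 SD present at all three visits would appear there as 0.07, 0.21 and 0.41. The currently planned linear model would give 0.29, 0.40 and 0.58.

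**Cost.** A few sentences, no new data and no change to the 160. The slope gains some precision. The contrasts can lose some: if the correlation among enrolled women is about 0.5, their variance is about 1.1 to 1.2 times that of the planned linear contrasts at days 30 and 90, and more if it is lower. That is the price of dropping the linearity assumption for the visit differences.
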